CONFIDENTIAL AND PROPRIETARY

Study Protocol—Device	Smith-Nephew
and performance of PICO 14 in the	Number: PICO14.WND.PRO.2019.03
	Version: 2.0, 12Sep2021
	Page: Page 36 of 131

5. OBJECTIVE(S).

5.1 PRIMARY OBJECTIVE.

To assess the functional clinical performance of PICO 14 NPWT system over 14 days therapy through the verification of delivery of negative pressure and wound exudate management.

5.2 SECONDARY OBJECTIVES.

Closed incisions ONLY

To assess clinical efficacy and safety of the PICO 14 NPWT system within 30 days of surgery through:

- Incidence of Surgical Site Infection (SSI) Superficial, deep. [CDC criteria].
- Incidence of Surgical site Complications (SSC) [as applicable: dehiscence (superficial/deep etc.), seroma, necrosis, hematoma, suture abscess].
- Condition of peri-wound skin assessed through visual inspection at 7, 14 and 30 days.
- Any pain experienced by the subject in relation to the PICO 14 system.
- Patient tolerability assessed by level of pain and level of satisfaction.
- Clinician acceptability assessed by ease of application and removal.
- Dressing wear time, dressing change frequency and dressing conformability.
- Scar quality measured by Patient and Observer Scar Assessment Scale (POSAS) score.

Chronic Wounds and dehisced surgical wounds ONLY

To assess clinical efficacy and safety of the PICO 14 NPWT system within 28 days therapy period through:

- Incidence of infection.
- Condition of peri-wound skin assessed through visual inspection at 7, 14, 21 and 28 days.
- Any pain experienced by the subject in relation to the PICO 14 system.

CONFIDENTIAL AND PROPRIETARY

Study Protocol—Device	Smith-Nephew
and performance of PICO 14 in the	Number: PICO14.WND.PRO.2019.03
	Version: 2.0, 12Sep2021
	Page: Page 37 of 131

Wound assessment:

- Appearance of the wound.
- Level of exudate.
- Wound pain.
- Size of wound (percentage reduction in area, depth, and volume).
- Patient tolerability assessed by level of pain and level of satisfaction.
- Clinician acceptability assessed by ease of application and removal.
- Dressing wear time, dressing change frequency and dressing conformability.

5.3 OTHER OBJECTIVES.

No other objectives.

5.4 SAFETY.

To assess Adverse Events and Device Deficiencies.

5.5 CLAIMS.

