- 11. Remove NPWT system as per procedure 9.4 for data chip collection.
- 12. Record pain score (VAS) and patient comfort since last assessment and pain score on dress removal.
- Follow procedure for removal, appropriate labelling and storage of pump for return to S&N.
- 14. Take photographs of the wound using camera provided by Sponsor (section 10.4.3) If any adverse events are observed or reported, they must be recorded as

CONFIDENTIAL AND PROPRIETARY

Study Protocol—Device	Smith-Nephew
and performance of PICO 14 in the	Number:
	PICO14.WND.PRO.2019.03
	Version: 2.0, 12Sep2021
	Page: Page 82 of 131

instructed in Section 12.

- 15. Follow procedure for removal, appropriate labelling and storage of pump for return to S&N.
- 16. Complete an Exit Form and exit the subject from the study stating the date and reason discontinuation. Standard care will be provided to the subject.

10.1.7 ADDITIONAL DRESSING CHANGE ASSESSMENT (DAY 1-27).

PICO 14 dressings are intended to be used for up to 7 days. Additional dressing change assessments will be completed if the dressing needs changing prior to Day 28 therapy period.

- 1. Record date and treatment setting.
- 2. Record reason for dressing change (e.g. routine, dressing saturated (exudate), strikethrough, leakage, pain, loss of vacuum, dressing got wet during shower/bathing, patient removed dressing, patient's request, other).
- 3. Record the use of concomitant medications.
- 4. Record reason if dressing is no longer in place (e.g. pain/discomfort from the dressing, patient removed, patient's request, adverse event, no vacuum, pump turned off, other).
- 5. Record if therapy has been interrupted since the previous assessment and how long.
- 6. Take photograph of dressing in place.
- 7. Assess subject satisfaction (overall performance of dressing, comfort, noise level, discreteness, portability, interference with daily living showering, sleeping, socialising, working).
- 8. Assess ease of removal.
- 9. Record pain score (VAS) since last assessment and on dressing removal.
- 10 A suitably qualified individual to complete assessment of wound complications. If any complications have occurred, details of this and additional procedures to be collected.
- 11 Assess the peri-wound skin.
- 12 Photograph the wound using the camera supplied by the Sponsor.

CONFIDENTIAL AND PROPRIETARY

Study Protocol—Device	Smith-Nephew
and performance of PICO 14 in the	Number: PICO14.WND.PRO.2019.03
	Version: 2.0, 12Sep2021

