and performance of PICO 14 in the	Number: PICO14.WND.PRO.2019.03
	Version: 2.0, 12Sep2021
	Page: Page 87 of 131

- O Granulation Tissue: Granulation tissue is the growth of small blood vessels and connective tissue to fill in full thickness wounds. Tissue is healthy when bright, beefy red, shiny and granular with a velvety appearance. Poor vascular supply appears as pale pink or blanched to dull, dusky red colour.
 - Skin intact or partial thickness wound
 - Bright, beefy red; 75% to 100% of wound filled &/or tissue overgrowth
 - Bright, beefy red; < 75% & > 25% of wound filled
 - Pink, &/or dull, dusky red &/or fills < 25% of wound
 - No granulation tissue present
- Epithelialization: Epithelialization is the process of epidermal resurfacing and appears as pink or red skin. In partial thickness wounds, it can occur throughout the wound bed as well as from the wound edges. In full thickness wounds, it occurs from the edges only. Use a transparent metric measuring guide with concentric circles divided into 4 (25%) pie-shaped quadrants to help determine the percent of wound involved and to measure the distance the epithelial tissue extends into the wound.
 - 100% wound covered, surface intact
 - 75% to < 100% wound covered &/or epithelial tissue extends to > 0.5 cm into wound bed
 - 50% to < 75% wound covered &/or epithelial tissue extends to < 0.5 cm into wound bed
 - 25% to < 50% wound covered
 - < 25% wound covered

- Level of Exudate
 - None;
 - Light;
 - Moderate;
 - Heavy
- Level of Pain since the last assessment (0-9; 0= no pain, 9 = maximum pain)
- Clinical judgement reference wound is clinically infected (Yes/No)

CONFIDENTIAL AND PROPRIETARY

Study Protocol—Device	Smith-Nephew
and performance of PICO 14 in the	Number: PICO14.WND.PRO.2019.03
	Version: 2.0, 12Sep2021 Page: Page 88 of 131

- Signs of clinical infection
 - None;
 - Wound static or deteriorating;
 - Increased exudate-secretion levels;
 - Increased pain;
 - Increased temperature around wound;
 - Discolouration of granulation tissue;
 - Friable granulation;
 - Tissue necrosis;
 - Local erythema;
 - Oedema;
 - Purulent drainage;
 - Odour;
 - Other

10.4.3 ASSESSMENT OF PERI-WOUND SKIN.

The surrounding skin will also be assessed by the above mentioned clinician. The clinician will assess whether the skin appears healthy or is fragile, inflamed, eczematous, dry/flaky, macerated or has erythema.

- Condition of peri-wound?
 - Normal
 - Erythematous
 - Oedematous
 - Eczematous

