Smith+Nephew's Global Biostatistics group will conduct the statistical analysis for this study. The subject data will be described and summarised using the baseline demographic and medical variables which include but are not limited to age, gender, ethnicity, medical and medication history, diagnostic factors as well as study process variables (e.g. AE and withdrawal(s)). Summary statistics will be given according to the nature of the variable, continuous or categorical. For continuous variables, the number of observations, mean, standard deviation, median, minimum, and maximum will be presented, while for categorical variables the number of observations, frequency, and percentages will be reported. Summary statistics will be presented by wound type and by country, where appropriate.

Primary, secondary, and exploratory outcome variables and derived variables will also be summarised accordingly. Parametric statistical tests will be used if the data is normally distributed and corresponding non-parametric tests will be considered if the data is not. Where necessary, suitable regression techniques will be used to adjust for confounding since the study is non-randomised. Unless otherwise stated, the results will be reported at 5% significance level and where appropriate 95% confidence intervals will be given.

11.2 ANALYSIS POPULATIONS.

- Full analysis set population (FAS), including all subjects who were recruited into the study and have at least one post-baseline visit.
- Safety Population (SAF), including all subjects who have received the study device.
- Per-Protocol Population (PP), including all subjects in the full analysis set who have no significant protocol deviations and met the inclusion/exclusion criteria.

Statistical analysis will be performed using each of the patient populations as follows: Analysis of the primary, secondary and exploratory efficacy objectives will be performed separately using both the Full Analysis Set and the Per Protocol Population. All safety analyses will utilize the Safety Population.

CONFIDENTIAL AND PROPRIETARY

Study Protocol—Device	Smith-Nephew
and performance of PICO 14 in the	Number: PICO14.WND.PRO.2019.03
	Version: 2.0, 12Sep2021 Page: Page 95 of 131
	rage 90 01 101

11.3 BASELINE DATA.

For chronic wounds and dehisced surgical wounds Day 0 (baseline) will be classified as the screening/ baseline visit. For closed surgical incisions Day 0 (baseline) will be classified as the operative day.

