- Level of pain on application, during wear and at dressing removal assessed by VAS scale over the 14 day treatment period.
- Patient satisfaction during wear assessed over the 14 day period. This includes leakage, feeling of moisture on the skin, odour control, level of protection, comfort and showerproof qualities.
- Ease of application and removal of the PICO 14 dressing.
- Dressing wear time.
- Dressing conformability
- Dressing change frequency and reason for dressing change.
- Clinician acceptability of PICO 14 system at discontinuation of therapy.
- Patient acceptability of PICO 14 system at discontinuation of therapy.

The POSAS consists of two parts: a Patient Scale and an Observer Scale. Each of the six items on both scales has a 10-point score. The lowest score is 1 and corresponds to the situation of normal skin (normal pigmentation, no itching etc.) and goes up to 10 indicating the worst imaginable. Total scores for both scales will be calculated separately by summing up the scores of each of the six items. An 'Overall Opinion' is scored separately of both patients and observers. Total scores and overall opinions will be summarised.

For incidence of SSC and incidence of SSI, binary variables indicating presence of/absence of will be defined. Total frequencies and number of subjects reporting each will be reported together with percentages.

CONFIDENTIAL AND PROPRIETARY

Study Protocol—Device	Smith-Nephew
management of south and obvenie wounds	Number: PICO14.WND.PRO.2019.03
	Version: 2.0, 12Sep2021 Page: Page 98 of 131

Condition of the peri-wound (e.g., healthy, fragile, inflamed, erythema, bruising, eczematous, dry/flaky, macerated) will be summarised.

Level of pain on dressing application will be collected at Day 0 and for each dressing change assessment, level of pain during wear will be collected throughout the 14 day period, and level of pain on dressing removal will be collected at routine dressing changes and at the end of study visit. These will be measured using a VAS scale and will be summarised by wound type.

Patient satisfaction will be measured by overall performance of the dressing, comfort, noise level, discreteness, portability and interference with daily living – showering, sleeping, socializing and working. Summary statistics will be given according to the nature of the variable, continuous or categorical.

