Ease of application, ease of establishing seal/negative pressure delivery, satisfaction of applying IP, knowing when to perform a dressing change and ease of removal will be reported by the clinician and frequencies will be summarised.

Dressing wear time (days) will be summarised as wear time per subject, by wound type and overall. Dressing change frequency will be summarised as the number of dressings per subject. Dressing conformability will be summarised as a categorical endpoint

Clinician and patient acceptability of PICO 14 system at discontinuation of therapy will be summarised through descriptive statistics and tabulated accordingly.

Chronic wounds and dehisced surgical wounds only:

Clinical performance and safety of the PICO 14 NPWT system over a 28 day therapy and no follow-up period to include:

- Incidence of clinical infection.
- Appearance of the wound in terms of tissue type and amount, exudate type and amount, skin condition surrounding the wound, peripheral tissue edema and induration.
- Condition of peri-wound skin assessed through visual inspection at 7, 14, 21 and 28 days.

CONFIDENTIAL AND PROPRIETARY

Study Protocol—Device	Smith-Nephew
and performance of PICO 14 in the	Number: PICO14.WND.PRO.2019.03
	Version: 2.0, 12Sep2021
	Page: Page 99 of 131

- Percentage reduction in area, depth and volume from baseline to day 7, day 14, day 21 and day 28.
- Level of pain on application, during wear and at dressing removal assessed by VAS scale over the 28 day treatment period.
- Patient satisfaction during wear assessed over the 28 day period. This includes leakage, feeling of moisture
 on the skin, odour control, level of protection, comfort and showerproof qualities.
- Ease of application and removal of the PICO 14 dressing.
- Dressing wear time.
- Dressing conformability
- Dressing change frequency and reason for dressing change.
- Clinician acceptability of PICO 14 system at discontinuation of therapy.
- Patient acceptability of PICO 14 system at discontinuation of therapy.

Incidence of clinical infection will be summarised at all study visits and dressing changes by wound type and overall.

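### For open wounds, section 11.6 summarises clinical infection only by visit and dressing change and defines no per-subject 28-day incidence

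*Combined protocol and SAP*

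**What the plan says.** **Objective and endpoint.** Section 5.2 introduces the open-wound objectives with "To assess clinical efficacy and safety of the PICO 14 NPWT system within 28 days therapy period through", and incidence of infection is the first item. Section 11.6 introduces the endpoints with "Clinical performance and safety of the PICO 14 NPWT system over a 28 day therapy and no follow-up period to include", and again infection comes first. Exclusion 12 in 7.3 keeps out wounds infected at entry.

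**Analysis for open wounds.** Section 11.6 gives one sentence: "Incidence of clinical infection will be summarised at all study visits and dressing changes by wound type and overall". It names no per-subject variable, denominator or confidence interval.

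**Analysis for closed incisions.** The same section says: "For incidence of SSC and incidence of SSI, binary variables indicating presence of/absence of will be defined", followed by "Total frequencies and number of subjects reporting each will be reported together with percentages".

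**Data collection.** Section 10.4.2 (Wound Assessment) holds the item "Clinical judgement reference wound is clinically infected (Yes/No". Table 10.1-1 marks the Wound Assessment for Days 0, 7, 14, 21 and 28 and for unscheduled or early-exit visits. The cell for additional dressing changes is blank. At those changes section 10.1.7 asks for something else: "A suitably qualified individual to complete assessment of wound complications".

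**The concern.** The objective asks how many subjects develop an infection during 28 days of therapy. Because infected wounds are excluded at entry, a first positive finding is a new infection, and each subject either has one or does not. A by-visit table answers a different question: how many wounds were infected on a given day among those assessed that day. Separate visit figures cannot in general be combined into a per-subject figure, because the table does not show whether positives at two visits come from the same subject.

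Infection is the first-listed clinical performance and safety endpoint for the open-wound cohort, which is most of the study. Without a subject-level definition, the report could carry several small visit percentages and no figure that answers the objective. Nothing in it could be set beside a per-patient rate such as the 16.6% that section 4.2 quotes from a chronic-wound study of the PICO system.

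**Working it through.** The documents state no infection rate or precision target for this endpoint, so there is no planned figure to reproduce. The calculation below shows how far by-visit and per-subject figures can differ.

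**Inputs from the documents**
- Scheduled post-baseline visits with the infection item: Days 7, 14, 21 and 28, so 4 (Table 10.1-1).
- Open-wound subjects: at least 4 types × 10 = 40, and at most 70 − 10 = 60 (section 7.1).
- Illustrative 28-day incidence C = 16.6% (section 4.2). That study's follow-up length is not given, so C is an assumption; 5% to 30% is used as a range.

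**Assumptions.** Infections are spread evenly over the four visits in (a) and (c), with a constant risk per visit in (b). The documents give no duration of infection, so three patterns are compared:
- (a) Positive at one visit, resolved by the next, subject stays: C/4 = 16.6/4 = 4.15%.
- (b) Subject leaves at the visit where infection is found, and that finding is counted: 1 − (1 − C)^(1/4) = 1 − 0.834^0.25 = 4.44%.
- (c) Infection persists and the subject stays: C × k/4 at visit k.

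| Pattern | Day 7 | Day 14 | Day 21 | Day 28 | Per subject |
|---|---|---|---|---|---|
| (a) | 4.15% | 4.15% | 4.15% | 4.15% | 16.6% |
| (b) | 4.44% | 4.44% | 4.44% | 4.44% | 16.6% |
| (c) | 4.15% | 8.30% | 12.45% | 16.60% | 16.6% |

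The ratio of per-subject to by-visit figure is 16.6/4.15 = 4.0 in (a) and 16.6/4.44 = 3.7 in (b). In (c) at Day 28 it is 1.

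**Range for pattern (b).** C = 5% gives 1.3% per visit, 10% gives 2.6%, 20% gives 5.4% and 30% gives 8.5%. The ratio runs from 3.9 down to 3.5.

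**Sensitivity to duration.** With onset uniform over 28 days and subjects staying, the visit figure is C × d/28 for an infection lasting d days, at visits on or after day d. Durations of 3, 7 and 14 days give 1.8%, 4.2% and 8.3%. At 3 days, only 4 × 3/28 × 16.6% = 7.1% of subjects are ever positive at a scheduled visit. At 7 days or more, all 16.6% are positive at some visit, although no single-visit row need show that.

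**Worked counts.** Take 8 of 40 subjects infected, two found at each visit, each leaving when found. The visit figures are 2/40 = 5.0%, 2/38 = 5.3%, 2/36 = 5.6% and 2/34 = 5.9%. The per-subject figure is 8/40 = 20.0% (exact 95% CI 9.1% to 35.6%).

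**Dressing changes.** Section 11.6 plans to summarise infection at dressing changes. Those made at the Day 7, 14 and 21 visits come with a full Wound Assessment and so have the item. Additional changes have a complications assessment only.

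**The case against.** **The sentence does not exclude a per-subject figure.** It keeps the word incidence and does not mention a percentage, which comes only from the general rule in 11.1: "while for categorical variables the number of observations, frequency, and percentages will be reported". Section 11 calls itself brief and defers detail to a later SAP. This stands to the extent that the plan leaves the measure undefined and does not forbid the right one. But an analyst following 11.6 as written would produce no 28-day figure. The closing word, overall, does not supply it: the same wording is used for wear time in 11.6 and for exposure in 11.8, where it means wound types pooled, not time points.

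**Subjects who stop because of infection.** A reader might infer that they are lost. The documents do not support that. The Wound Assessment is marked for unscheduled and early-exit visits. Section 10.2 asks for a full exit visit where possible and says that withdrawal from treatment does not by itself end participation. An infection can also be recorded as an adverse event, although 11.8 does not single infection out. What stands is narrower: subjects who leave the study drop out of later denominators, and 11.6 does not say whether unscheduled or exit findings enter the table.

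**Visit figures always read low, or count an infection twice.** Neither follows. Pattern (c) reaches the full incidence at Day 28, and dropout among uninfected subjects could raise a visit percentage. A positive at two visits appears in two separate figures; double counting would need a pooling that is not planned.

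**Dressing changes have no infection data.** This is also too strong. The gap concerns additional changes, and there it is the specific Yes/No item that is missing.

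**Conclusion.** The concern holds as a missing definition with a practical consequence. Section 11.6 yields no per-subject 28-day infection incidence for open wounds, although the objective calls for one and the same section counts subjects for SSI and SSC. It also leaves open how unscheduled and early-exit findings count, and it plans a dressing-change summary whose Yes/No item is not scheduled at additional changes.

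The possible understatement is about 3.5 to 4 times if each infection is positive at one visit only or the subject leaves when it is found, with assumed incidences from 5% to 30%. It is larger for infections shorter than a week. It is absent at Day 28 if infections persist and subjects stay. The documents do not indicate which pattern to expect.

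This is a descriptive secondary endpoint, and the primary pressure analysis is unaffected. The change should still be made before the SAP is finalised, because the data are largely collected already.

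**What to change.** 1. In 11.6, add a binary per-subject endpoint for chronic and dehisced wounds: any clinical infection of the reference wound from Day 0 to Day 28 or exit. Count findings from scheduled visits, additional dressing changes, unscheduled and early-exit visits, and adverse event records.
2. Report number and percentage with a 95% CI, by wound type and combined. Use FAS and PP, as 11.2 assigns for efficacy objectives, and also the Safety Population, because the endpoint is partly a safety measure and FAS requires a post-baseline visit. The Safety Population analysis is an addition to 11.2 and should be stated as such.
3. Keep the by-visit table as supportive, show the number assessed at each visit, and state whether unscheduled and exit visits are included.
4. Add the infected Yes/No item from 10.4.2 to the additional dressing change form in 10.1.7, and mark it in Table 10.1-1.

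The cost is one form field and some SAP wording. The reported infection figure will usually be higher than the single-visit figures.
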